## 4. OBJECTIVES AND ENDPOINTS

Objectives	Endpoints
Primary	
To compare the effect of 6 months use of the CIS on adherence to ELLIPTA maintenance therapy when both the subject and the HCP are supplied with data from the maintenance sensor versus no data supplied to the subject and HCP (Arm 1 vs Arm 5)	Percentage of ELLIPTA doses taken (daily adherence  ) between the beginning of month 4 and the end of month 6 as determined by the maintenance sensor

Objectives	Endpoints
Secondary	

To compare the effect of 6 months use of the CIS on adherence to ELLIPTA maintenance therapy for the following aspects of the CIS:
 
 
• Maintenance data only supplied to subjects versus no data supplied to the subject (Arm 2 vs Arm 5)
 
• Rescue and Maintenance data supplied to subject and HCP versus no data supplied to the subject and HCP (Arm 3 vs Arm 5)
 
• Rescue and Maintenance data only supplied to subject versus no data supplied to the subject (Arm 4 vs Arm 5)
 
	
 
• Percentage of ELLIPTA doses taken (daily adherence) between the beginning of month 4 and the end of month 6 as determined by the maintenance sensor
 

To compare the effect of the CIS on adherence to ELLIPTA maintenance therapy of the individual CIS treatment arms versus no data supplied to the subject and HCP.
	
 
• Percentage of ELLIPTA doses taken (daily adherence) between the beginning of month 1 and the end of month 3
 
• Percentage of ELLIPTA doses taken (daily adherence) between the beginning of month 1 and the end of month 6
 

To evaluate the effect of 6 months use of the CIS on a subject's rescue medicine usage
	
 
• Percentage of rescue free days measured between the beginning of month 4 and the end of month 6 as determined by the rescue sensor records of date, time, and number of inhaler actuations.
 
• Total rescue use measured between the beginning of month 4 and the end of month 6 as determined by the rescue sensor records of date, time, and number of inhaler actuations.
 

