## 11. STATISTICAL CONSIDERATIONS

### 11.1. Hypothesis

The main purpose of the study is to compare the effect of 6 months use with the CIS on adherence to ELLIPTA maintenance therapy with adherence to ELLIPTA maintenance therapy without CIS use (sensor alone), in subjects with poorly controlled asthma. This study aims to demonstrate the superiority of the CIS on adherence to Relvar/Breo ELLIPTA with an app compared to Relvar/Breo ELLIPTA (with sensor alone). The primary endpoint is mean percentage of ELLIPTA doses taken (daily adherence) between Months 4 and 6 as determined by the maintenance sensor daily adherence over the last three months of the study period (between months 4 to 6).

The test for the primary treatment comparison will be a test between Arm 1 versus Arm 5. This will be based on a two-sided hypothesis testing approach: the null hypothesis is the difference between Arm 1 and Arm 5 is equal to zero. The alternative hypothesis is that the difference is not equal to zero. The hypotheses associated with the statistical test of the primary endpoint are written below:

$$H_0: T_i - T_j = 0$$

(where i = Arm 1 and j = Arm 5) The null hypothesis: that the difference in response between Arm 1 and Arm 5 is zero.

$$H_a: T_i - T_j \neq 0$$

The alternative hypothesis: that the difference is not zero.

Other comparisons of interest for the primary endpoint are the individual comparisons of Arms 2, 3 and 4 with Arm 5 in order to obtain estimated mean treatment differences and 95% confidence intervals. This will be a descriptive comparison to inform on the relative benefits of the individual aspects of the CIS and no formal inference is planned.

The effect on adherence to maintenance therapy between arms with HCP and no HCP interaction, and arms with rescue medication use feedback versus none, will be also assessed.

The comparisons of interest for the other secondary and safety endpoints are as stated above for the primary endpoint. Arms 1, 2, 3 and 4 will be individually compared to Arm 5, as relevant to the endpoint, in order to obtain estimated mean treatment differences and 95% confidence intervals. This will be a descriptive comparison and no formal inference is planned.

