The effect on adherence to maintenance therapy between arms with HCP and no HCP interaction i.e. Arm 1 v Arm 2 and Arm 3 v Arm 4, and arms with rescue medication use feedback versus none i.e. Arm 1 v Arm 3 and Arm 2 v Arm 4, will be also assessed.

The comparisons of interest for the other secondary and safety endpoints are as stated above for the primary endpoint. Arms 1, 2, 3 and 4 will be individually compared to Arm

5, as relevant to the endpoint, to obtain estimated mean treatment differences, 95% confidence intervals and p-values. This will be a descriptive comparison and no formal inference is planned.

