## **5.2. Baseline Definitions**

Baseline adherence will be the percentage of ELLIPTA doses taken (daily adherence) during the last 28 days of the run-in period prior to randomisation. This will be determined using the randomisation date. A minimum of 14 run-in days prior to randomisation will be required to determine baseline adherence otherwise it will be set to missing. Any missing intermittent daily adherence data will be imputed as non-adherent i.e. the participant will be assumed to have not taken their treatment within the 24-hour time period/window, where there is no evidence of a medical device incident having occurred. Missing data due to a medical device incident such as,

- device failure
- technical failure of the ELLIPTA maintenance sensor
- data transmission failure,

will be assumed to be missing at random (MAR). For each participant the baseline percentage adherence measure will be calculated as the number of days a participant is adherent divided by the number of days without medical device incident within the baseline assessment period \* 100. See Section [10.2.2](#) Definitions of Assessment Windows for Adherence and Rescue Medication Use Analyses, for the definition of the baseline assessment period.

Baseline rescue free days will be the percentage rescue free days (RFDs) during the last 28 days of the run-in period prior to randomisation. This baseline will be determined in the same manner as the adherence baseline.

Where baseline assessments are determined from the randomisation visit, no unscheduled assessments will be considered as the baseline value.

Where baseline assessments are determined from the screening visit, Visit 1 will be used and no unscheduled screening visits will be considered as the baseline value.

If time is not collected, Day 1 assessments are assumed to be taken prior to first dose and used as baseline.

Parameter	Study Assessments Considered as Baseline			Baseline Used in Data Display
	Visit 1 Screening	Study Days -28 to -1	Randomisation Visit, Study Day 1 (Pre-Dose)	
Efficacy				
ELLIPTA Adherence Endpoints (%)		x		% adherence from Day -28 to Day -1
Rescue Free Days (RFDs) (%)		x		% RFDs from Day -28 to Day -1
Total Rescue Use (TRU) (puffs)		x		Total use from Day -28 to Day -1
ACT Total score			x	Randomisation
SGRQ Total score			x	Randomisation
ASUI Total score			x	Randomisation
PAM-13 Total score	x			Screening
BMQ Total score	x			Screening
MARS-A Total score	x			Screening

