#### **7.2.2.1. Summary Measure**

The rescue medicine summary measures are:

- The mean difference in percentage of rescue free days between the treatment arms will be estimated from an Analysis of Covariance (ANCOVA) model allowing for effects due to randomised treatment, baseline rescue-free, duration of run-in (visits), country, gender, and age (years).
- The mean total rescue use for the treatment arms will be summarised using summary statistics (n, mean, SD, median, min, max) for each treatment arm for each Month separately, and totalled Month 4 – 6.

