### Model Results Presentation

Summary statistics (mean, standard deviation, median, minimum, maximum) of the primary endpoint will be provided, based on the observed percentages.

The adjusted means for each treatment and the estimated treatment difference for the treatment comparisons of Arm 1 versus Arm 5, Arm 2 versus Arm 5, Arm 3 versus Arm 5 and Arm 4 versus Arm 5 will be presented together with the 95% confidence interval for the differences and corresponding p-values from

the multiple imputation procedure.

Endpoint / Variables
Total rescue use measured between the beginning of month 4 and the end of month 6 as determined by the MDI rescue sensor
Summary

The endpoint will be summarised using descriptive statistics (n, mean, SD, median, min, max) for each treatment arm.
 
To explore the effect of 6 months use of the CIS on a participant's rescue medicine usage, the following displays will be presented,
 
 
Summary statistics (n, mean, SD, median, min, max) of Total rescue use measured between the beginning of month 4 and the end of month 6 as determined by the MDI rescue sensor
 
Total rescue use will be summarized by each individual month (Month 1 – Month 6) and then displayed as a total between month 4 – 6.
 

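### Total rescue use is the only secondary efficacy endpoint for which the SAP plans no comparison of Arms 1 to 4 with Arm 5

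*SAP*

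**What the plan says.** Protocol Section 4 lists as a secondary endpoint "Total rescue use measured between the beginning of month 4 and the end of month 6 as determined by the rescue sensor records"; SAP 2.2 and 7.2.2 carry it over. The objective it serves is "To evaluate the effect of 6 months use of the CIS on a subject's rescue medicine usage".

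Protocol 11.1 sets the comparisons: "The comparisons of interest for the other secondary and safety endpoints are as stated above for the primary endpoint". The sentence on the arms begins "Arms 1, 2, 3 and 4 will be individually compared to Arm 5, as relevant to the endpoint, in order to obtain estimated mean treatment", and what it promises for each arm is an estimated difference with its 95% confidence interval. SAP 2.4 repeats this, with the same relevance qualifier, "to obtain estimated mean treatment differences, 95% confidence intervals and p-values". Both documents call the comparison descriptive and plan no formal inference from it.

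For total rescue use the methods sections stop short of that. SAP 7.2.2.1 has "The mean total rescue use for the treatment arms will be summarised using summary statistics", and SAP 7.2.2.5 has "The endpoint will be summarised using descriptive statistics (n, mean, SD, median, min, max) for each treatment arm", shown by month and for months 4 to 6. Table 2.14 uses shell EFF_T1, whose mock-up has no row for a difference, an interval or a p-value. SAP 5.2 defines a baseline total over Day -28 to Day -1.

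**The concern.** Participants are randomised 1:1:1:1:1 and Arm 5 is the control, so an objective about the effect of the CIS on rescue use is a between-arm question. Two endpoints serve that objective. One of them, percentage of rescue-free days, is modelled with each CIS arm against Arm 5. The other, total use, is reported as five sets of summary statistics with no planned estimate of effect and no interval.

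The two endpoints do not measure the same thing. Take a participant who goes from 8 to 4 puffs every day (an illustration, not a figure from the documents). Over the 84 days of months 4 to 6 the total falls from 672 to 336 puffs, while rescue-free days stay at 0% throughout. An effect in heavy users would show in the total and not in rescue-free days.

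**Working it through.** **1. Is total rescue use treated differently from the other secondary endpoints?** The secondary efficacy endpoints and their planned comparison with Arm 5 are:

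| Endpoint | SAP section | Contrast with Arm 5 |
|---|---|---|
| Adherence, months 4-6 (Arms 2-4; Arm 1 is the primary) | 7.2.1.5.1 | Difference, 95% CI, p-value |
| Adherence, months 1-6 | 7.2.1.5.2 | Difference, 95% CI, p-value |
| Adherence, months 1-3 | 7.2.1.5.3 | Difference, 95% CI, p-value |
| Rescue-free days, months 4-6 | 7.2.2.5 | Difference, 95% CI, p-value |
| Total rescue use, months 4-6 | 7.2.2.5 | None |
| ACT change from baseline | 7.2.3.4.1 | Difference, 95% CI, p-value |
| Three ACT responder endpoints | 7.2.3.4.2 to 7.2.3.4.4 | Odds ratio, 95% CI, p-value |

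It is the only one without a contrast. The exploratory ASUI and SGRQ endpoints (SAP 7.3.3.5) also get contrasts with Arm 5.

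**2. Is the omission declared?** SAP Table 1 lists changes from the protocol analysis down to the wording of the composite ACT endpoint, but not this. Where the SAP wants summaries only, it expressly rules out formal analysis: 7.3.3.4.5 for PAM-13, MARS-A and BMQ, and 7.3.4.5 for FeNO and PEF. There is no such statement in 7.2.2.5. In the list of displays, Table 2.13 (rescue-free days) carries a note to present Arms 1 to 4 against Arm 5; Table 2.14 carries none.

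**3. What precision is available?** The documents give no SD or effect size for total rescue use, so there is no planned figure to reproduce for it. The sample-size basis (Protocol 11.2.1: 76 per arm, SD 28, difference 15, two-sided 5%) reproduces for the primary endpoint:

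- 15 / (28 x sqrt(2/76)) = 3.30, and 3.30 - 1.96 = 1.34, giving power of 91.0% against the stated 90%.
- Smallest significant difference: 1.96 x 28 x sqrt(2/76) = 8.9 against the stated 9.

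For total rescue use, in SD units, the 95% half-width of one arm minus Arm 5 is 1.96 x sqrt((2/n) x (1 - rho^2)), where rho is the correlation between baseline and months 4-6 use:

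- n = 76, unadjusted: 1.96 x sqrt(2/76) = 0.318
- n = 76, rho = 0.5 (assumed): 0.318 x sqrt(0.75) = 0.275
- n = 76, rho = 0.7 (assumed): 0.318 x sqrt(0.51) = 0.227
- n = 86 (432/5), unadjusted: 1.96 x sqrt(2/86) = 0.299

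**4. Can the raw total be modelled as it stands?** No. The intercurrent-event rules in SAP 7.2.2.3 and the derivation in SAP 10.5.3.2 cover rescue-free days only. No rule says how a puff total is formed when the sensor stops, the participant withdraws or a device incident occurs. Suppose a participant uses 4 puffs a day and the sensor stops at the end of month 5 (Day 140). Recorded days in the window are 140 - 85 + 1 = 56, and the raw total is 4 x 56 = 224 instead of 4 x 84 = 336. Per recorded day it is 4 in both cases. Observation time also varies without any loss: SAP Table 5 needs only 14 days for a 28-day baseline and lets month 6 end at V10 for a completer.

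**The case against.** The strongest reply is that the commitment is conditional. Both documents say the comparison is made where relevant to the endpoint, both call it descriptive, and Protocol 11.4 leaves specific details to the RAP. The same sentence covers safety endpoints, for which Protocol 11.4.2 plans only counts and percentages, and the binary ACT endpoints get odds ratios, not mean differences. The per-arm treatment of total use is also the same in the methods text, the list of displays and the mock shell, so it may be deliberate. This shows that the sentence leaves latitude. It does not show that the latitude was used: neither document says a comparison is irrelevant to total rescue use, and SAP 2.4 still states the general commitment.

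A reader might infer that the randomised comparison is lost altogether, or that the rescue objective cannot be answered. The documents do not support that. Reported n, mean and SD allow a crude interval, (mean_k - mean_5) +/- 1.96 x sqrt(SD_k^2/n_k + SD_5^2/n_5), and rescue-free days give a modelled comparison for the same objective. Nor is the baseline total unused: SAP 5.2 defines it for display, and the shell has a baseline row. It simply enters no model.

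A further fair objection is that an ANCOVA on the raw total would attach a confidence interval to an outcome that falls when recording stops. That stands, and it shapes the fix.

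**Conclusion.** The point holds as a gap between the stated comparisons and the specified analysis of one secondary endpoint. What is missing is a pre-specified, baseline-adjusted difference from Arm 5 with its 95% interval for each of the four CIS arms. It is not a dropped confirmatory test, because none was promised, and the primary comparison, its alpha and the sample size are untouched.

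In size, the plan leaves the reader a crude interval of about +/-0.32 SD per contrast at 76 per arm, where baseline adjustment could give about +/-0.28 or +/-0.23 SD. Those figures assume equal SDs, an approximately normal mean difference and correlations of 0.5 or 0.7 that are not in the documents. They show what adjustment could add and do not predict the result. The crude interval also inherits whatever lost recording does to the raw totals.

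**What to change.** In SAP 7.2.2.1 and 7.2.2.5, add for months 4 to 6 total rescue use the Arm k minus Arm 5 difference (k = 1 to 4) with a 95% confidence interval and a p-value labelled descriptive. Estimate it by ANCOVA with the covariates used for rescue-free days (arm, run-in visits, country, gender, age), the Day -28 to Day -1 total rescue use as the baseline term, and robust standard errors.

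Before modelling, put both the baseline and the months 4 to 6 totals on a recorded-time scale. One option is puffs per day with sensor data, excluding device-incident and post-discontinuation days; another is to extend the rescue-free-days imputation rules to this endpoint. Add the CIS-arm-versus-Arm-5 block of shell EFF_T4 to Table 2.14, keep the monthly descriptive rows, and correct the table title, which names the maintenance sensor.

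The cost is SAP wording, one derivation rule, one model and one table block, all from data already collected, plus four more unadjusted descriptive p-values. Robust standard errors protect the interval, not the mean, from a few heavy users, so the medians should stay in the table. If the sponsor does intend summaries only, the lesser remedy is to say so in 7.2.2.5, log it with a reason in SAP Table 1 and amend SAP 2.4.

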### 7.2.2.3. Strategy for Intercurrent (Post-Randomisation) Events

It is assumed that salbutamol MDI rescue medication use does not permanently discontinue for asthmatic participants, regardless of whether they are used in addition to maintenance therapy or not.

The following steps in [Table 4](#) will be applied sequentially when deriving the rescue free days endpoint. See Section [10.5.3.2](#) MDI Device Sensor Assessments for full details of the missing data imputations process.

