**Table 5 Sensor Data Assessment Windows**

Sensor Data Assessment Windows		
Analysis Month	Analysis Period	
	Beginning Timepoint	Ending Timepoint
Baseline	Latest of either Day -28 or day after Visit 1 (minimum of 14 days must be present to create a baseline)	Day -1 (Day prior to randomisation)
1	Day 1 (Day of randomisation)	Day 28 or discontinuation from adherence/rescue assessment if within month 1
2	Day 29	Day 56 or discontinuation from adherence/rescue assessment if within month 2
3	Day 57	Day 84 or discontinuation from adherence/rescue assessment if within month 3
4	Day 85	Day 112 or discontinuation from adherence/rescue assessment if within month 4
5	Day 113	Day 140 or discontinuation from adherence/rescue assessment if within month 5
6	Day 141	Earliest of either day of visit 10, Day 168 or discontinuation from adherence/rescue assessment if within month 6 if participant is a completer  OTHERWISE  Day 168 or discontinuation from adherence/rescue assessment if within month 6
Note: 'Discontinuation from adherence/rescue assessment' occurs at the earliest of premature discontinuation from use of the ELLIPTA /MDI sensor, premature discontinuation of ELLIPTA (for adherence measures), or premature withdrawal from the study.		

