### Percentage of Rescue Free Days Endpoint

The following observations from the sensor and eCRF will be required to determine the above Days and the differences between missing at random due to device/sensor incident and non-adherent days.

- Device malfunction date
- Sensor malfunction date
- Permanent discontinuation of MDI rescue sensor
- First and last individual sensor synchronisation dates

The first and last individual sensor synchronisation dates will be provided in the sensor dataset. These dates will be used to assess whether missing observations are due to rescue free days or data being missing at random due to device/sensor malfunction.

For each Analysis Month, the Observed MDI rescue free days (%) for that month will be calculated as follows:

$$\text{Monthly observed MDI rescue free days (\%)} = \left( \frac{D4}{D5 - D2 - D3} \right) \times 100$$

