### 10.6.2. Handling of Missing Data

Element	Reporting Detail
General	
 
Missing data occurs when any requested data is not provided, leading to blank fields on the collection instrument: 
 
These data will be indicated by the use of a “blank” in participant listing displays. If all data for a specific visit are missing, the visit will be excluded from the display.
 
Answers such as “Not applicable” and “Not evaluable” are not considered to be missing data and will be displayed as such.
 
 
 

MMRM Analysis	
 
All the available assessments taken at scheduled visits will be included in the repeated measures models in which missing data are not explicitly imputed but the correlation between visits for all participants is used to adjust the estimate of treatment effect considering any missing data.
 

Rescue Free Days Endpoint	
 
Handling of missing sensor data is detailed in Section 7.2.2.3 Strategy for Intercurrent (Post-Randomisation) Events, as well Section 10.5.3.2 MDI Device Sensor Assessments.
 

ACT	
 
Handling of missing ACT data is detailed in Section 7.2.3.3 Strategy for Intercurrent (Post-Randomisation) Events.
 

Other PROs	
 
Handling of missing PRO data is detailed in Section 7.3.3.4 Strategy for Intercurrent (Post-Randomisation) Events, as well in Section 10.5.3.3 Patient Reported Outcomes.
 

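### Total rescue use is summarised as recorded puffs with no allowance for days the MDI sensor did not record, and its months 4 to 6 value is not fully defined

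*SAP*

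**What the plan says.** Protocol Section 4 lists the secondary endpoint "Total rescue use measured between the beginning of month 4 and the end of month 6 as determined by the rescue sensor". SAP Section 5.2 gives its unit as puffs.

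SAP Section 7.2.2.1 states "The mean total rescue use for the treatment arms will be summarised using summary statistics", for each month and totalled over months 4 to 6. Section 7.2.2.5 repeats this: "Total rescue use will be summarized by each individual month", followed by a months 4 to 6 total. There is no model.

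The shell for this table in Section 10.9 asks instead for an average over months 4 to 6.

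Rules for unrecorded sensor days exist, but for the companion endpoint. The Table 4 steps in Section 7.2.2.3 "will be applied sequentially when deriving the rescue free days endpoint". Step 1 of Section 10.5.3.2 reads "For each Analysis Month, the Observed MDI rescue free days (%) for that month will be calculated as follows" and removes device-incident and post-discontinuation days from the denominator. The only rescue row in Section 10.6.2 is headed "Rescue Free Days Endpoint".

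The Table 5 note says that discontinuation from assessment "occurs at the earliest of premature discontinuation from use of the ELLIPTA /MDI sensor", among other events. Section 7.2.2.3 assumes that "salbutamol MDI rescue medication use does not permanently discontinue for asthmatic participants".

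**The concern.** A percentage of rescue free days can be computed on whatever days were observed. A puff count cannot be read that way: it grows with the number of recorded days. Measurement ends when the MDI sensor stops, while the SAP assumes that inhaler use goes on. Two participants with the same use can therefore get different totals because their sensors ran for different lengths of time.

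The derivation is also open. Two programmers could reach different months 4 to 6 values from the same records, depending on what they do with a month that has no sensor data and on whether they follow the text or the shell.

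At stake is the reading of one descriptive table.

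**Working it through.** The documents give no numeric target for this endpoint, so there is no plan figure to reproduce. The check asks which rules reach total rescue use, and then how large the gap is in the SAP's own examples.

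**Which rules apply**

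| Rule for unrecorded days | Place in SAP | Endpoint covered |
|---|---|---|
| Intercurrent-event rules (Table 4) | 7.2.2.3 | Rescue free days |
| Denominator D5 − D2 − D3 | 10.5.3.2, Step 1 | Rescue free days |
| Imputation (MAR or jump to reference) | 10.5.3.2, Steps 2 to 4 | Rescue free days |
| Combining months, weights | 10.5.3.2, Step 5 | Rescue free days |
| Missing-data row | 10.6.2 | Rescue free days |

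None covers total rescue use.

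**Size**

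Assume constant use of 2 puffs per day (my assumption; the percentages do not depend on it). Shortfall = 1 − recorded days / comparison days.

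1. *One month, 20 of 28 days recorded:* 1 − 20/28 = 28.6%, or 40 puffs instead of 56.
2. *Sensor stopped after day 20 of month 5 (10.5.3.2, Step 4, first example).* Recorded days are 28, 20 and 0. The comparison is the full 84 days, because Step 5 carries rescue free days to the end of the period.
   - Month 6 as zero: 28 + 20 + 0 = 48; 1 − 48/84 = 42.9% (96 puffs instead of 168).
   - Average of months with data: (56 + 40)/2 = 48 per month instead of 56; 1 − 48/56 = 14.3%.
   - Missing month voids the value: nothing is reported.
   - This participant also leaves the study after day 5 of month 6. Against 28 + 28 + 5 = 61 days in study, the zero reading is 1 − 48/61 = 21.3% low.
3. *Completer example (same step): month 6 ends on day 27, r1 = 15, r2 = 12.* Recorded days are 28 + 28 + 15 = 71. Days counted by r4 are 28 + 28 + 27 = 83. The shortfall is 1 − 71/83 = 14.5%, for a total or a three-month average alike, since no month is wholly unobserved. This is measured against time in study. Table 5 can end month 6 when the sensor stops, which gives a window of 71 days and no shortfall within it.
4. *Mock listing EFF_L2, Arm 3, month 1:* 18 + 9 = 27 observed days, one device-incident day, 29 puffs. 1 − 27/28 = 3.6%; scaled, 29 × 28/27 = 30.1.
5. *Baseline:* Table 5 accepts 14 days. At constant use, a 14-day total is half a 28-day total.

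**Which denominator for a rate**

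Section 10.5.3.2 describes D5 both as D1 + D2 + D3 + D4 and as the days up to the Table 5 end point. In the 20-day month these can differ:

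- D5 = 28 and D3 = 8 give 28 − 8 = 20 observed days, and 40/20 = 2.0 puffs per day.
- D5 = 20 from Table 5, with D3 = 8 counted on the calendar, gives 20 − 8 = 12, and 40/12 = 3.3.
- D1 + D4 (days with recorded use plus rescue-free days) is 20 on either reading.

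For months 4 to 6 in example 2, 96/48 = 2.0 puffs per day, and 2.0 × 84 = 168, which recovers full use.

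**The case against.** The protocol defines the endpoint by what the rescue sensor records, and the SAP's unit is puffs, so a summary of recorded puffs follows the protocol. That stands. Puffs per observed day is a different measure with its own assumption, so it belongs beside the total, not in its place.

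The SAP's general conventions point towards observed-data summaries. Section 10.4.2 defines n as participants with non-missing values, the shell prints n for every month, and Section 10.6.1 includes available data from withdrawn participants where possible. Counting an empty month as zero is therefore the least supported reading, and 42.9% is the result of that reading alone. The conventions still do not decide between skipping the month and voiding the months 4 to 6 value.

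Table 5 and the assumption of continued MDI use are not contradictory: one says when measurement ends, the other describes behaviour.

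Sensor loss is partly visible elsewhere. EFF_L2 lists device-incident and post-discontinuation days beside the puffs, Table 1.9 and EFF_T21 tabulate sensor status and incidents by arm, and the Table 1.40 footnote says what its zero category contains. None of these puts observed days in the total rescue use table.

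A reader might infer that the comparison with Arm 5 is biased, since Protocol Section 5.1 has Arms 1 to 4 connect through a phone and Arm 5 through a home hub. Equal loss cannot be assumed, but the documents give no loss rate by arm, so neither size nor direction can be stated.

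**Conclusion.** The point holds, with low consequence. Total rescue use carries no adjustment for unrecorded days, and the rule for a wholly unobserved month is not given. A month recorded for 20 of 28 days is 28.6% low. In the SAP's first example the months 4 to 6 value is 42.9% low, 14.3% low or missing, depending on an unstated choice. All figures rest on constant daily use and on illustrative rows in the SAP, not on trial data.

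Two stronger readings are not supported. A reader might take the completer example as losing 14.5% of its own analysis window; the 83 days come from r4, and the Table 5 window can be 71 days with nothing missing. A reader might also infer that the rescue findings as a whole are unreliable. No test or p-value rests on total rescue use, and the modelled rescue endpoint, rescue free days, has its own denominator and imputation.

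**What to change.** - Keep the protocol total. Beside it, report puffs per observed day = puffs recorded / (D1 + D4) for baseline, each month and months 4 to 6, set to missing when D1 + D4 = 0.
- Show observed days by arm in the same table.
- State whether a wholly unobserved month counts as zero, is skipped, or makes the months 4 to 6 value missing.
- Make Section 7.2.2.5 and the Section 10.9 shell agree on total or average.
- State the downside: the rate assumes that use on unobserved days matches the participant's observed use. This differs from the jump-to-reference assumption for rescue free days in Arms 3 and 4.

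Two side items do not carry the point. The titles of Table 2.14 in Section 10.8.6 and of its shell name the maintenance sensor where the endpoint uses the MDI sensor, a clerical correction. Splitting device-incident and post-discontinuation days from true zeros in Table 1.40 is optional.

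The cost is SAP wording, one derived variable and an observed-days row. D1 and D4 are already counted for the MDI sensor in Section 10.5.3.2, so no new data are needed.
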